11.1 Efficacy Variables

Primary endpoint

The primary endpoint is the PFS rate at 12 weeks, defined as the proportion of patients alive and progression-free at Week 12. Patients will be progression-free if they have no evidence of progressive disease (defined according to RECIST guidelines, version 1.1) from the start of treatment to Week 12.

Tumor response will be assessed at 6-week intervals during the first treatment cycle using the RECIST criteria version 1.1. Each patient will be assigned one of the following categories: 1) complete response (CR), 2) partial response (PR), 3) stable disease (SD), or 4) progressive disease (PD). Patients who died from any cause or discontinued the study for any reason without a post-screening or Week 12 tumor assessment will be considered as failing to respond to treatment.

Secondary efficacy endpoints

Secondary efficacy endpoints are as follows:

- Objective response rate, defined as the proportion of patients whose best overall response is either CR or PR according to RECIST version 1.1. The best overall response is the best response recorded during the first 12-week treatment cycle.
- Disease control rate, defined as the proportion of patients with a documented CR, PR and SD during the first 12-week treatment cycle according to RECIST version 1.1.
- Duration of overall tumor response, defined as the interval between the date of the first observation of tumor response (CR or PR) and the date of disease progression or death.
- Progression free survival, defined as the time from the date of first administration of study drug to objective tumor progression by RECIST version 1.1 or death due to any cause, whichever occurs first.
- Overall survival, defined as the time from the date of first administration of study drug to death from any cause.
- Time to progression, defined as the time from the date of first administration of study drug to objective tumor progression by RECIST version 1.1.

Patient Reported Outcome endpoint:

The PRO endpoint is as follows:

- European Organization for Research and Treatment of Cancer QLQ-C30 and the EORTC QLQ-LC13.

Pharmacokinetic endpoints:

For Stage 1, PK endpoints will be derived for intensively sampled PK profiles by non-compartmental methods and include:

- C_{\max} : peak concentration
- C_{trough} : trough plasma concentration
- T_{\max} : peak time
- AUC_{τ} : area under the plasma concentration-time curve over the 8-hour dosing interval
- $T_{1/2}$: terminal half-life

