14.2.1 Analysis Populations

The primary analysis will be performed on the evaluable population. The evaluable population will consist of all enrolled patients who receive at least one dose of antroquinonol and have a valid baseline tumor assessment. A valid baseline assessment is defined as a readable scan (one in which the images are of high enough quality to permit accurate assessment of the tumor) performed within 14 (\pm 7) days of the date of first administration of study drug. For the efficacy analysis, enrollment will continue until the target number of evaluable patients has been enrolled.

The full analysis set (FAS) and PPS will be used for supportive efficacy analyses. The FAS will consist of patients in the evaluable population who have at least one post-baseline tumor

assessment. The PPS will consist of patients in the FAS who do not have major protocol violations.

The PK population will consist of patients in the first stage who have an evaluable PK profile, defined as a profile from which at least one of the PK parameters stated as endpoints can be estimated, and no protocol deviations that would affect the PK of antroquinonol.

The PopPK population will consist of patients with at least two plasma concentrations and sufficient and reliable dosing histories.

The Safety population will comprise all patients who are treated with at least one dose of study drug.

The PRO population will consist of all patients who have completed the QoL Questionnaire on Day 0 and on at least one occasion after the first administration of study drug.

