14.2.2.1 Primary Efficacy Analysis

The primary endpoint is the PFS rate at 12 weeks, defined as the proportion of patients alive and progression-free at Week 12. Patients will be progression-free if they have no evidence of progressive disease (defined according to RECIST guideline, version 1.1) from the start of treatment to Week 12. An evaluable patient who died from any cause or discontinued the study for any reason without a post-screening or Week 12 tumor assessment will be considered as failing to respond to treatment.

The primary analysis will be performed on the evaluable population as defined in [Section 14.2.1](#). The FAS and PPS (as defined in [Section 14.2.1](#)) will be used for supportive efficacy analyses. The PFS rate together with a two-sided 95% exact confidence interval (CI) will be calculated for the evaluable population, FAS and PPS.

The primary analysis will follow the two-stage procedure as specified in [Section 14.1](#).

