14.2.2.2 Secondary Efficacy Analysis

The FAS and PPS will be used for the secondary efficacy analyses. The secondary efficacy endpoints comprise the following: ORR, DCR, DR, PFS, OS and TTP.

The ORR is defined as the proportion of patients whose best overall response is either CR or PR according to RECIST version 1.1. The best overall response is the best response recorded during the first 12-week treatment cycle.

The DCR is defined as the proportion of patients with a documented CR, PR and SD during the first 12-week treatment cycle according to the RECIST version 1.1. For both ORR and DCR, 95% two-sided CIs will be presented.

The DR is defined as the interval between the date of the first observation of tumor response (CR or PR) and the date of disease progression or death. The DR will be summarized using Kaplan-Meier methods and displayed graphically where appropriate. The DR will be calculated for the subgroup of patients with tumor response (CR or PR).

If the number of patients with a documented CR or PR is small then only descriptive statistics or listings will be presented.

Progression-free survival is defined as the time from the date of first administration of study drug to objective tumor progression by RECIST version 1.1 or death due to any cause, whichever occurs first. The censoring rule for PFS will be described in the SAP.

Overall survival is defined as the time from the date of first administration of study drug to death from any cause. The censoring rule for OS will be described in the SAP.

Time to progression is defined as the time from the date of first administration of study drug to objective tumor progression by RECIST version 1.1. The censoring rule for TTP will be described in the SAP.

Objective response rate and DCR will be reported with category counts, percentage and 95% CIs. PFS, OS and TTP will be evaluated using Kaplan-Meier estimates and curves will be generated based on these estimates.

Time-to-event endpoints will be re-analyzed when all patients have completed the Extension Phase.

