 - If the positive FDG-PET at follow-up corresponds to a pre-existing site of disease on CT that is not progressing on the basis of the anatomic images, this is not PD.

Missing assessments and not-evaluable designation

When no imaging/measurement is done at all at a particular time point, the patient is not evaluable at that time point. If only a subset of lesion measurements are made at an assessment, usually the case is also considered not evaluable at that time point, unless a convincing argument can be made that the contribution of the individual missing lesion(s) would not change the assigned time point response. This would be most likely to happen in the case of PD.

For example, if a patient had a baseline sum of 50 mm with three measured lesions and at follow-up only two lesions were assessed, but those gave a sum of 80 mm, the patient will have achieved PD status, regardless of the contribution of the missing lesion. If one or more target lesions were not assessed either because the scan was not done, or could not be assessed because of poor image quality or obstructed view, the Response for Target Lesions should be “Unable to Assess” since the patient is not evaluable. Similarly, if one or more non-target lesions are indicated as ‘not assessed’, the response for non-target lesions should be “Unable to Assess” (except where there is clear progression). Overall response would be “Unable to Assess” if either the target response or the non-target response is “Unable to Assess” (except where this is clear evidence of progression) as this equates with the case being not evaluable at that time point.

Time point response

It is assumed that at each protocol specified time point, a response assessment occurs. Table 1 below provides a summary of the overall response status calculation at each time point for patients who have measurable disease at baseline.

When patients have non-measurable (therefore non-target) disease only, Table 2 is to be used.

Table 1 Time point response: patients with target (+/-non-target) disease

Target lesions	Non-target lesions	New lesions	Overall response
CR	CR	No	CR
CR	Non-CR/non-PD	No	PR
CR	Not evaluated	No	PR
PR	Non-PD or not all evaluated	No	PR
SD	Non-PD or not all evaluated	No	SD
Not all Evaluated	Non-PD	No	NE
PD	Any	Yes or No	PD
Any	PD	Yes or No	PD
Any	Any	Yes	PD

CR = complete response, PR = partial response, SD = stable disease, PD = progressive disease, and NE = inevaluable.

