Table 2 Time point response: patients with non-target disease only

Non-target lesions	New lesions	Overall response
CR	No	CR
Non-CR/non-PD	No	Non-CR/non-PD ^a
Not all evaluated	No	NE
Unequivocal PD	Yes or No	PD
Any	Yes	PD

CR=complete response, PD=progressive disease, and NE=inevaluable.

a ‘Non-CR/non-PD’ is preferred over ‘stable disease’ for non-target disease since SD is increasingly used as endpoint for assessment of efficacy I some trails so to assign this category when no lesions can be measured is not advised.

Evaluation of best overall response

The best overall response is the best response recorded from the start of the study drug until the end of treatment. Post-treatment assessments will not be considered in determination of best overall response. No new therapies are permitted by the protocol. If any other therapy is instituted during the study, the patient will be censored from the BOR assessment. Given the use of PFS as the primary efficacy endpoint, and the short timeframe of this study, confirmation of PR and CR is not required in this study.

The *best overall response* will be determined by statistical programming once all the data for the patient is known.

Special notes on response assessment

When nodal disease is included in the sum of target lesions and the nodes decrease to ‘normal’ size (< 10 mm), they may still have a measurement reported on scans. This measurement should be recorded even though the nodes are normal in order not to overstate progression should it be based on increase in size of the nodes. As noted earlier, this means that patients with CR may not have a total sum of ‘zero’ on the case report form (eCRF). In studies where confirmation of response is required, repeated ‘NE’ time point assessments may complicate best response determination. The analysis plan for the study must address how missing data/assessments will be addressed in determination of response and progression. For example, in most studies it is reasonable to consider a patient with time point responses of PR-NE-PR as a confirmed response.

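### The Week 12 failure rule has two readings for a patient who leaves after a stable Day 42 scan with no Week 12 scan, so the primary success count is not uniquely defined

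*Protocol*

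**What the plan says.** The primary endpoint is the proportion of evaluable patients alive without progression at Week 12. Section 14.2.2.1 defines success by absence of evidence: "Patients will be progression-free if they have no evidence of progressive disease" between the start of treatment and Week 12. It then adds a failure rule for patients who died or "discontinued the study for any reason without a post-screening or Week 12 tumor assessment will be considered as failing to respond to treatment". Section 11.1 and the synopsis use the same phrase, "discontinued the study for any reason without a post-screening or Week 12 tumor assessment", and Section 11.1 assigns each patient CR, PR, SD or PD, with no category for a scan that cannot be evaluated.

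On-treatment scans are due on Days 42 and 84 (Sections 9.1.1 and 11.2.1). The evaluable population in Section 14.2.1 is "all enrolled patients who receive at least one dose of antroquinonol and have a valid baseline tumor assessment", so no post-baseline scan is needed to be in the denominator.

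Two passages send matters to the SAP. Section 14.2.2.2 says "The censoring rule for PFS will be described in the SAP", which concerns the time-to-event secondary endpoint. Appendix 1 recognises missing scans ("When no imaging/measurement is done at all at a particular time point, the patient is not evaluable at that time point") and adds: "The analysis plan for the study must address how missing data/assessments will be addressed in determination of response and progression".

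**The concern.** The Week 12 rate is the only endpoint with a formal decision rule, and every decision in Sections 14.1 and 14.3 compares a count of successes with a fixed cut-off. The protocol states the failure rule for that count itself, in three places, in words that can be taken two ways for one identifiable kind of patient: a drop-out with a Day 42 scan and no Week 12 scan. The same data could then give 8/30 or 9/30 in a stratum, or 14/60 or 15/60 overall. In an open-label single-arm trial the choice of reading should not be left until the data can be seen.

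A second, weaker point concerns patients still on study. The failure rule names only those who died or discontinued. A patient on study with no earlier progression and a missing or unreadable Day 84 scan is outside it and, read literally, has no evidence of progression.

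**Working it through.** **1. The two readings.** A Week 12 scan is itself a post-screening scan.

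- *Lacking either scan* reduces to lacking the Week 12 scan, so the post-screening term does no work. The patient with SD on Day 42 and no Week 12 scan is a **failure**.
- *Lacking both scans* reduces to lacking any post-screening scan, so the Week 12 term does no work. The same patient is not failed and, if alive, is a **success** under the no-evidence wording.

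Each reading makes one term redundant, so grammar does not decide. Nor does the text say whether an End of Study scan can serve as the Week 12 assessment. Appendix 1 states only that "Post-treatment assessments will not be considered in determination of best overall response", which is a different endpoint.

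**2. The plan's own figures.** Inputs from Section 14.1: stratum, continue if at least 2/15, positive if at least 9/30; overall, continue if at least 3/20, positive if at least 15/60; null rate 15%; target rates 40% (stratum) and 35% (overall). For the overall design, the clause that also looks at the strata is left out. With first-stage size n1, cut-off a, total n and final cut-off r,

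P(positive | p) = Σ over x ≥ a of Bin(x; n1, p) × P[Bin(n − n1, p) ≥ r − x].

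| | p | Result | Stated |
|---|---|---|---|
| Stratum, type I error | 0.15 | 0.0276 | 2.8% |
| Stratum, power | 0.40 | 0.9049 | 90.5% |
| Overall, type I error | 0.15 | 0.0279 | 2.8% |
| Overall, power | 0.35 | 0.9558 | 95.6% |

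All four reproduce. The design arithmetic is not in question.

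**3. How far the reading could move the error rate (illustration).** The protocol gives no missing-scan rate. Assumptions: constant hazard; 15% is the rate with complete scans; a share m of patients event-free at Day 42 lacks a Week 12 scan, independently of outcome.

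- Event-free at Day 42: √0.15 = 0.3873. Event between Day 42 and Day 84: 0.3873 − 0.15 = 0.2373.
- Patients whose status depends on the reading at m = 5%: 30 × 0.3873 × 0.05 = 0.58 per stratum; 60 × 0.3873 × 0.05 = 1.16 overall.
- If they fail: p = 0.15 × (1 − m). If they are credited: p = 0.15 + 0.2373 × (1 − d) × m, where d is the share of Day 42 to 84 events that are deaths. Deaths fail on every reading, so d = 0 is the upper bound.

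| m = 5% | p | Stratum | Overall |
|---|---|---|---|
| Counted as failures | 0.1425 | 2.0% | 1.8% |
| Credited, d = 0 (upper bound) | 0.1619 | 4.3% | 5.0% |
| Credited, d = 25% | 0.1589 | 3.9% | 4.4% |
| Credited, d = 50% | 0.1559 | 3.5% | 3.8% |

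The bound depends on the constant hazard. If instead 30% or 60% are event-free at Day 42, with m = 5% and d = 0, p is 0.15 + 0.15 × 0.05 = 0.1575 or 0.15 + 0.45 × 0.05 = 0.1725. The error is then 3.7% or 6.1% per stratum and 4.1% or 7.9% overall.

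**The case against.** - **The failure reading is the natural one.** The endpoint asks for status at Week 12, and a patient who left after Day 42 has no observed status then. This stands as the better reading. It does not make the sentence unambiguous: the other reading is grammatically open and is backed by the no-evidence definition beside it.
- **The SAP will deal with missing scans.** For on-study patients this largely stands. All analyses fall under a SAP, and Appendix 1 tells it to address missing assessments. A reader might infer that the plan credits every on-study patient without a Day 84 scan. The documents do not support that: the protocol's rule fails to exclude such a patient, but the SAP, not available here, may do so. For drop-outs the objection does not stand, because the protocol has already fixed a rule and the explicit deferral in Section 14.2.2.2 covers only time-to-event censoring.
- **The error figures overstate.** This stands in part. They are upper bounds unless deaths after Day 42 are removed, they pool drop-outs with on-study patients, and they take 15% as a rate with complete scans. If 15%, 35% and 40% were meant for the count as scored, the stated error and power hold unchanged. A reader might infer that the stated 2.8% is wrong or that the trial runs at 5%. Neither follows.
- **An End of Study scan may supply the missing assessment.** Sometimes it can. That visit falls 4 weeks after the last dose, or earlier if new treatment is about to start (Section 9.1.3.8), so its scan may or may not land near Week 12. This is a reason to state a window, not evidence that the gap is closed.

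**Conclusion.** The concern holds for the drop-out clause. For a patient with SD on Day 42 who leaves alive without a Week 12 scan, the protocol does not uniquely say whether the patient is a failure or a success, although failure is the better reading. The on-study gap is secondary and may be closed in the SAP.

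The consequence is certain in kind: such patients remain in the denominator, and one of them can decide 2/15, 3/20, 9/30 or 15/60. The size is unknown. Under the assumptions set out above with 5% missing, crediting them gives at most 4.3% per stratum and 5.0% overall, or 3.9% to 3.5% and 4.4% to 3.8% if 25% to 50% of the Day 42 to 84 events are deaths. The cut-offs and the stated operating characteristics need no change. This should be fixed, but it is a matter of wording and not a flaw in the design.

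**What to change.** In Sections 11.1 and 14.2.2.1 and the synopsis, state the rule positively:

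*An evaluable patient is progression-free at Week 12 only if alive with a central-review CR, PR or SD at an assessment within a pre-specified Week 12 window and no earlier PD; every other evaluable patient, on study or discontinued, counts as not progression-free.*

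Add that an End of Study scan counts only if it falls in that window. Use the same rule at the interim looks and the final analysis, and replace the phrase about failing to respond with *not progression-free*, since the endpoint is progression status and not response. The window width, and any sensitivity analysis using later scans, are for the sponsor to choose in advance.

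The cost is a few lines of text and no extra procedures. The observed rate, and so power, may be slightly lower. If an assumed 5% of true successes lack a usable scan, the rates become 0.40 × 0.95 = 0.38 and 0.35 × 0.95 = 0.3325, and power is 86.2% per stratum (stated 90.5%) and 92.5% overall (stated 95.6%).

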14.2.2.2 Secondary Efficacy Analysis

The FAS and PPS will be used for the secondary efficacy analyses. The secondary efficacy endpoints comprise the following: ORR, DCR, DR, PFS, OS and TTP.

The ORR is defined as the proportion of patients whose best overall response is either CR or PR according to RECIST version 1.1. The best overall response is the best response recorded during the first 12-week treatment cycle.

The DCR is defined as the proportion of patients with a documented CR, PR and SD during the first 12-week treatment cycle according to the RECIST version 1.1. For both ORR and DCR, 95% two-sided CIs will be presented.

The DR is defined as the interval between the date of the first observation of tumor response (CR or PR) and the date of disease progression or death. The DR will be summarized using Kaplan-Meier methods and displayed graphically where appropriate. The DR will be calculated for the subgroup of patients with tumor response (CR or PR).

If the number of patients with a documented CR or PR is small then only descriptive statistics or listings will be presented.

Progression-free survival is defined as the time from the date of first administration of study drug to objective tumor progression by RECIST version 1.1 or death due to any cause, whichever occurs first. The censoring rule for PFS will be described in the SAP.

Overall survival is defined as the time from the date of first administration of study drug to death from any cause. The censoring rule for OS will be described in the SAP.

Time to progression is defined as the time from the date of first administration of study drug to objective tumor progression by RECIST version 1.1. The censoring rule for TTP will be described in the SAP.

Objective response rate and DCR will be reported with category counts, percentage and 95% CIs. PFS, OS and TTP will be evaluated using Kaplan-Meier estimates and curves will be generated based on these estimates.

Time-to-event endpoints will be re-analyzed when all patients have completed the Extension Phase.

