
In addition to within-stratum hypothesis testing, this study is also designed to investigate the PFS rate at 12 weeks in the overall (unselected) population. If less than three patients are alive and progression-free at Week 12 in the first 20 evaluable patients and, the criterion for continuing the individual stratum are not met, then the accrual for all strata will be discontinued. Otherwise, a maximum of 40 additional evaluable patients will be entered (depending on whether any individual stratum is closed). Fifteen or more patients alive and progression-free at Week 12 out of the maximum 60 evaluable patients would warrant further study.
 
The overall design has a significance level of 2.8% (probability of falsely declaring the regimen with a 15% PFS rate at 12 weeks to warrant further study) and power 95.6% (probability of declaring the regimen with a 35% PFS rate at 12 weeks in the overall population to warrant further study).
 
Efficacy:
 
Except for the primary efficacy analysis, there will be no formal statistical testing. All data will be summarized and listed as appropriately. All efficacy endpoints will be evaluated in both the overall (unselected) population and within-stratum.
 
The primary analysis will be performed on the evaluable population. The evaluable population will consist of all enrolled patients who receive at least one dose of antroquinonol and have a valid baseline tumor assessment. A valid baseline assessment is defined as a readable scan performed within 14 (\pm 7) days of the date of first administration of study drug. For the efficacy analysis, enrollment will continue until the target number of evaluable patients has been enrolled.
 
The full analysis set (FAS) and per-protocol set (PPS) will be used for supportive efficacy analyses. The FAS will consist of patients in the evaluable population who have at least one post-baseline tumor assessment. The PPS will consist of patients in the FAS who do not have any major protocol violations.
 
The primary analysis will follow the two stage procedure, as specified in the sample size section. All secondary efficacy endpoints will be reported with category counts, percentage and 95% confidence interval (CI). All time-to-event endpoints, PFS, OS and TTP will be evaluated using Kaplan-Meier estimates and curves will be generated based on these estimates.
 
Safety:
 
All patients who are treated with at least one dose of study drug will be evaluated for safety. Safety data will be summarized for the overall (unselected) population and within-stratum. There will be no formal statistical analysis of safety data. Demographic and Screening data will be listed and summarized, as appropriate. All AEs will be coded using the Medical Dictionary for Regulatory Activities, graded using the NCI CTCAE version 4.03 and listed by patient. Treatment-emergent AEs will be summarized by treatment, severity and causal relationship to study drug. Any serious AEs will be listed separately. System organ class and preferred terms within each body system will be used for frequency summaries. Clinical laboratory data, vital signs and ECG data will be listed by patient and summarized, as appropriate.
 
Patient Reported Outcome:
 
The PRO population will consist of all patients who have completed the QLQ on Day 0 and on at least one occasion after the first administration of study drug. All data will be summarized and listed, as appropriate. Patient Reported Outcome data will be summarized for the overall (unselected) population and within-stratum.
 
Pharmacokinetics:
 
Non-compartmental PK analysis will be performed for the PK population. The PK population will consist of patients in the first stage who have an evaluable PK profile, defined as a profile from which at least one of the PK parameters stated as endpoints can be estimated, and no protocol deviations that would affect the PK of antroquinonol. Descriptive statistics will be presented for all PK parameters. The PopPK methods will be used to estimate exposure metrics for patients with at least two plasma concentrations and sufficient and reliable dosing histories.
 
Tumor biomarkers:
 
The predictive value of tumor biomarkers will be assessed in appropriate subgroup analyses. Full details of this analysis will be provided in the Statistical Analysis Plan.
		

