Patients will attend study visits on Days 0, 14, 28, 42, 56 and 84 during the first 12-week treatment cycle, every 4 weeks during the second, third, and fourth treatment cycles (Extension Phase); and every 12 weeks during subsequent treatment cycles (Extension Phase). The study-specific procedures include: physical examination, vital signs, 12-lead ECG, performance status, clinical laboratory tests, AEs, concomitant medication and patient compliance. The schedule of assessments is presented in [Table 9.1](#).

Patients discontinuing study drug will attend an End of Study (EOS) Visit, 4 weeks after the last administration of study drug. In the event that a patient is scheduled to start a new treatment earlier than 3 weeks after the last dose of study drug, the EOS Visit should occur before the start of the new treatment and the reason documented.

Intensive PK sampling will be performed on Days 0 and 28 in all patients enrolled in Stage 1. Sparse PK sampling will be performed on Days 28, 42, and 56 in all patients enrolled in Stage 2.

All patients who withdraw from the study drug, but consent to be followed up for survival status, will be followed up by telephone contact every 3 months, for a maximum of 6 months from the date of last administration of study drug or death, whichever occurs first.

Tumor assessments will be performed at Screening, Days 42 and 84 using the Response Evaluation Criteria in Solid Tumors (RECIST) criteria, version 1.1 (see [Appendix 1](#)). Tumor assessments will be performed every 12 weeks during the Extension Phase.

The primary efficacy endpoint is progression-free survival (PFS) rate at 12 weeks, which is defined as the proportion of patients alive and progression-free at Week 12. Patients will be progression-free if they have no evidence of progressive disease (defined according to RECIST guidelines, version 1.1) from the start of treatment to Week 12.

The study uses a two-stage design seeking to detect a true PFS rate of more than 35% in the overall (unselected) population and 40% within the KRAS tumor mutation positive and negative strata. Thirty evaluable patients (15 in each stratum) will be treated initially (Stage 1), with expansion to a maximum of 60 evaluable patients (Stage 2). The rules for continuing the overall study and individual stratum are provided in [Section 14.2](#).

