9.1.3.8 End of Study (EOS) Visit (± 7 days)

Patients will attend an EOS Visit, 4 weeks after the last administration of study drug. In the event that a patient is scheduled to start a new treatment earlier than 3 weeks after the last dose of study drug, the EOS Visit should occur before the start of the new treatment and the reason documented.

- Record concomitant medications
- Perform physical examinations
- Obtain vital signs
- Perform ECOG performance status evaluation
- Perform 12-Lead ECG examinations
- Perform clinical laboratory tests (hematology, biochemistry, and urinalysis)
- Tumor assessments (radiological and clinical tumor assessments). Tumor assessment does not need to be performed at the EOS Visit if this was conducted at the Day 84 Visit. For patients participating in the Extension Phase, the tumor assessment does not need to be performed at the EOS Visit if it has been assessed within 8 weeks of the EOS Visit.
- Perform drug accountability
- Record AE and grade possible toxicity. Safety follow-up data may be collected by telephone contact every 3 months after the EOS Visit.
- Calculate patient compliance
- Perform EORTC QLQ

- All patients who withdraw from the study drug, but consent to be followed up for survival status, will be followed up by telephone contact every 3 months, for a maximum of 6 months from the date of last administration of study drug or death, whichever occurs first.

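### OS, PFS, ORR and DCR are assigned to sets that drop patients who die or are lost before any post-baseline scan, which flatters these four results

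*Protocol*

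**What the plan says.** Section 14.2.2.2 covers ORR, DCR, DR, PFS, OS and TTP and states: "The FAS and PPS will be used for the secondary efficacy analyses". It names no other set for them.

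The synopsis defines the first of these sets: "The FAS will consist of patients in the evaluable population who have at least one post-baseline tumor assessment". Section 14.2.1 repeats the definition, and the PPS is the part of the FAS without major violations. Both places give FAS and PPS a supportive role and run the primary analysis on the evaluable population, which needs one dose and a valid baseline scan but no later scan.

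Section 14.2.2.1 keeps patients without the required scan in the primary analysis as failures. The rule applies to "An evaluable patient who died from any cause or discontinued the study for any reason without a post-screening or Week 12 tumor assessment".

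On timing, section 9.1.1 says: "Tumor assessments will be performed at Screening, Days 42 and 84 using the Response Evaluation Criteria". The first scheduled post-baseline scan is therefore Day 42. On survival, section 14.2.2.2 says: "Overall survival is defined as the time from the date of first administration of study drug to death from any cause". Section 9.1.1 provides for status to be collected without imaging: "All patients who withdraw from the study drug, but consent to be followed up for survival status, will be followed up by telephone contact".

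**The concern.** OS starts at first dose and needs only a death date. PFS also starts at first dose and counts death from any cause. Requiring a scan for entry to the analysis conditions both on surviving to that scan. This is immortal-time bias: the earliest deaths are deleted although they are known from telephone follow-up and from SAE reporting (section 13.10.5). For ORR and DCR, a patient with no scan cannot be a responder or be documented as controlled, so removing that patient can only raise the rate.

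The population makes early attrition plausible: stage IV disease, two to four prior lines in the main route of entry, and ECOG 0 to 2 allowed (section 9.3.1). In a single-arm trial no control group shares the bias, so it passes straight into the estimates used to judge further development. Time-to-event PFS would also rest on a different denominator from the primary 12-week PFS rate.

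**Working it through.** **The plan's own figures.** The protocol gives no number on this point. The nearest are the operating characteristics in section 14.1, which concern the evaluable population. With P = Σ P(X₁ = x) · P(X₂ ≥ r − x), summed over the first-stage counts x that allow continuation:

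- Stratum (15 then 30 patients, continue at 2 or more, success at 9 or more): 0.0276 at 15% and 0.9049 at 40%, against the stated 2.8% and 90.5%.
- Overall (20 then 60 patients, continue at 3 or more, success at 15 or more): 0.0279 at 15% and 0.9558 at 35%, against the stated 2.8% and 95.6%.

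All four agree, and the present point leaves them unchanged.

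**Which endpoints are affected.**

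| Endpoint | Patient who dies before any scan | Patient lost alive before any scan |
|---|---|---|
| ORR, DCR | leaves denominator, rate rises | leaves denominator, rate rises |
| OS, PFS | event deleted, estimate rises | early censored time deleted, little or uncertain effect |
| DR | not affected: every responder has a scan | not affected |
| TTP | no bias claimed: death is not an event and censoring is left to the SAP | no bias claimed |

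**ORR and DCR.** Let d of the 60 evaluable patients have no post-baseline scan, none of them a responder or controlled. Then FAS rate = evaluable rate × 60/(60 − d). The values of d are assumptions. The example counts are also assumed: 21/60 controlled (35.0%, exact 95% CI 23.1 to 48.4) and 6/60 responders (10.0%).

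| d | 60/(60 − d) | DCR in FAS (95% CI) | ORR in FAS |
|---|---|---|---|
| 3 | 1.05 | 21/57 = 36.8% (24.4 to 50.7) | 6/57 = 10.5% |
| 6 | 1.11 | 21/54 = 38.9% (25.9 to 53.1) | 6/54 = 11.1% |
| 12 | 1.25 | 21/48 = 43.8% (29.5 to 58.8) | 6/48 = 12.5% |
| 18 | 1.43 | 21/42 = 50.0% (34.2 to 65.8) | 6/42 = 14.3% |

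**OS.** Assume exponential survival with true median m months. Day 42 is 42/30.4375 = 1.38 months.

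- Share dead by Day 42: F = 1 − 0.5^(1.38/m).
- If a share q of those deaths has no scan, the FAS curve after Day 42 is S(t)/(1 − qF). Its median solves S(t) = 0.5(1 − qF), so the shift is −m · log₂(1 − qF).
- At q = 1 the shift is exactly 1.38 months, whatever the median.

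| m (months) | F | Deaths by Day 42 of 60 | Shift, q = 0.25 | Shift, q = 0.5 | Shift, q = 1 |
|---|---|---|---|---|---|
| 4 | 0.213 | about 13 | 0.32 | 0.65 | 1.38 |
| 6 | 0.147 | about 9 | 0.32 | 0.66 | 1.38 |
| 9 | 0.101 | about 6 | 0.33 | 0.67 | 1.38 |
| 12 | 0.077 | about 5 | 0.33 | 0.68 | 1.38 |

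PFS moves in the same direction because deaths before a scan are PFS events. Its size was not computed separately.

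**The case against.** The strongest case against is that the effect may be small and is partly visible.

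- **EOS scans.** Early stoppers are to attend an EOS Visit with a tumor assessment, and the exemption is narrow: "Tumor assessment does not need to be performed at the EOS Visit if this was conducted at the Day 84 Visit". Many of them will enter the FAS. This stands and pushes the effect toward the lower rows. It does not help a patient who has died, and section 9.3.4 accepts that EOS assessments may go undone.
- **Life expectancy.** Section 9.3.1 requires at least 3 months, which should give fewer early deaths than a constant hazard implies. This stands for size only. The rows with d = 18 and q = 1 are upper ends, not expectations.
- **Sampling error.** At d = 3 or 6 the shift lies well inside the confidence interval. That is true, but the error always runs in the favourable direction and is avoidable.
- **Containment.** The 12-week PFS rate is reported in all three sets (section 14.2.2.1), so a reader can see one such gap. That does not correct OS, ORR or DCR.
- **Deferral to the SAP.** Section 14.2.2.2 does not expressly forbid a further analysis in the evaluable population. But it defers only the censoring rules, and censoring cannot restore patients outside the set. The unselected population in section 14.2.2 refers to KRAS status and is not an analysis set.

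**Conclusion.** The point holds and should be fixed. As written, the analysis set removes known early deaths from OS and PFS and certain non-responders from the ORR and DCR denominators, while the primary analysis keeps the same patients as failures. The direction for ORR and DCR follows from the definitions. For OS and PFS it follows from the excluded deaths, not from patients lost alive.

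The size is not known. A multiplier of 1.05 to 1.11 on the rates assumes 3 to 6 of 60 patients without a scan. A gain of 0.3 to 0.7 months in median OS assumes exponential survival and a quarter to a half of the deaths before Day 42 left unscanned. The harm is confined to descriptive estimates: type I error, power, the primary endpoint and the stage rules are untouched.

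**What to change.** In section 14.2.2.2, make the evaluable population the main set for PFS, ORR, DCR and OS, so that all four share the primary denominator. The Safety (all treated) population would also remove the bias for OS; whichever is chosen should be named. State that patients with no post-baseline scan count as non-responders without disease control, and that deaths before a scan count as OS and PFS events. Keep FAS and PPS as supportive, the role that the synopsis and section 14.2.1 already give them. Carry the same wording into the SAP, with the censoring of patients lost alive specified there as already planned.

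The cost is one or two sentences and somewhat less favourable secondary figures. No additional data are needed.
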